Currently, there is only one randomized, controlled trial published in 1999 that compared the use of diuretics alone versus the combination of diuretics and albumin in cirrhotic patients.³ This was a single center conducted in Italy where the investigators used potassium canrenoate and furosemide as diuretics in combination with albumin (25%) 12.5 grams daily. The doses of diuretics used were per center protocol and based on patient clinical response. The results from their study showed that the cumulative rate of response to diuretic treatment of ascites was higher (90.5% vs. 74.7%) (p< 0.05) and length of hospital stay was shorter (p< 0.05) in the group of patients that received diuretics and albumin versus diuretics alone. Although the results were favorable with the use of albumin, the external validity of this study is minimal since it was a single center conducted in Italy in 1999.

III. Study Aims

a. The purpose of this single center, prospective study is to compare the efficacy of two strategies for diuresis in patients with cirrhosis, the use of furosemide (Lasix®) alone versus the combination of furosemide (Lasix ®) and albumin (25%).

IV. Administrative Organization

 a. All research regarding this project will be performed at Rush University Medical Center (RUMC). There will be no inclusion of outside study sites, laboratories, or data management centers.

V. Methods and Materials

- a. Trial Design and sample size
 - i. We will perform a single-center, prospective study with data collected as result of standard of care at RUMC. Patients who are 18 years of age and older, have diagnosed cirrhosis, and present to RUMC with fluid retention will be identified by the Hepatology and/or Surgery attending and be screened for inclusion in the study. Each patient will be randomized into one of the two cohorts and will have 50% chance of being placed into either cohort.
 Cohort 1 will receive furosemide (Lasix) 40 to 80 mg IVP BID for at least 48 hours and cohort 2 will receive combination of furosemide (Lasix) 40 to 80 mg
 - ii. A sample size of 150 patients for this study was estimated based on the previously published study by Gentilini P and colleagues.³ The estimation was based on a success rate of 70% in patients receiving diuretics alone and 90% in patients receiving diuretics plus albumin (alpha = 0.05; beta =0.25).

IVP BID and albumin (25%) 12.5 grams BID for at least 48 hours.

b. Process of Consent

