i. This study is a prospective study so consent from the patient will be obtained prior to enrollment. To obtain consent, the physician will explain the purpose of the study, associated risk and benefits, and answer any additional questions or concerns the patient may ask. If patient decides to enroll in the study, the physician will provide them with the appropriate consent form and all signed forms will be in a securely locked filing cabinet.

c. Participants

i. Adult patients (age ≥18 years old) who have cirrhosis and present to RUMC with fluid retention (ascites, edema, or pulmonary effusions).

d. Inclusion/Exclusion Criteria

 Inclusion criteria: Adult patients (age ≥18 years old), diagnosis of cirrhosis and presents with fluid retention as defined as ascites, edema, or pulmonary effusions requiring diuresis.

ii. *Exclusion criteria*: Patients who are younger than 18 years of age or currently pregnant or who presents with a serum creatinine greater than 2 mg/dL will be excluded.

e. Outcomes

- i. *Primary outcome*: Urine output greater than or equal to 0.5 ml/kg/hour over 24 hours or reduction in weight defined as weight loss of 1 kilogram or greater in a 24-hour period. (While urine output is the best measure for diuretic efficacy, it can often be an unreliable measurement due to patient's not collecting urine properly. Therefore, changes in weight after initiation of diuretic therapy is often used as a surrogate marker for the efficacy of the diuretic therapy, regardless of patient weight at baseline. Several heart failure trials use a change in weight as the endpoint for assessing diuretic efficacy, and this endpoint is also commonly used in clinical practice. Therefore, that is why this endpoint was chosen for this study.)
- ii. **Secondary outcome:** Change in renal function as defined by a chance in serum creatinine from admission to discharge, hospital length of stay, 30-day readmission rates, and patient survival at 6 months and 1 year.

VI. Risk/Benefit Assessment

a. Potential Risks

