a. Data collection will take place on a data collection tool, which will be separate from PHI and will not contain identifiers. RedCAP will be used for data collection and storage. Patient confidentiality will be maintained by recording only de-identified data onto the data collection form. Although the data collected and stored in REDCap will be exported for analysis, the exported data will contain no unique, patient-identifying information. Access will only be available to the research investigators.

Data collected from the electronic medical record at RUMC will include:

- 1. Patient demographics
- 2. Daily lab results including chemistry panel, INR, liver function tests, renal function tests
- 3. Physician's rating of patient's edema (if applicable)
- 4. Dose, frequency, and administration of furosemide (Lasix ®) and/or albumin

VIII. Analysis Plan

a. Statistical analysis will be performed with SPSS statistical package. Patient characteristics will be described using frequencies, means ± standard deviations or medians ± interquartile ranges. Student's t-test will be used to compare continuous variables. Comparisons between groups or categories will be made using chi-squared test. The threshold for statistical significance will be p<0.05.

IX. Literature Cited

- 2. American Association for the Study of Liver Diseases (AASLD): Practice guidelines for the management of adult patients with ascites due to cirrhosis 2012. Hepatology 57(4), 2013.

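### Renal change is measured from admission and the creatinine limit is applied at presentation, not at randomisation: this costs precision and leaves a gap in eligibility, but does not bias the arm comparison

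*Combined protocol and SAP*

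**What the plan says.** All references are to the combined protocol and SAP.

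- **Eligibility (V.d.ii).** Any patient "who presents with a serum creatinine greater than 2 mg/dL will be excluded". No sampling window is given and no repeat value before randomisation is required.
- **Secondary outcomes (V.e.ii).** The list opens with a change in "serum creatinine from admission to discharge, hospital length of stay". The renal outcome has a written start, admission. Length of stay has none.
- **Order of events (V.a.i, V.b.i).** Adults with cirrhosis who "present to RUMC with fluid retention will be identified by the Hepatology and/or Surgery attending and be screened for inclusion in the study" are then randomised, and "consent from the patient will be obtained prior to enrollment". Presentation and randomisation are thus separate events, and nothing limits the time between them.
- **Baseline.** None is defined for creatinine. The only wording that ties a measurement to the start of treatment, "changes in weight after initiation of diuretic therapy", belongs to the rationale for the weight part of the primary outcome (V.e.i).
- **Data (VII.a).** The items collected include "Daily lab results including chemistry panel, INR, liver function tests, renal function tests".
- **Analysis (VIII.a).** "Student's t-test will be used to compare continuous variables", with no baseline covariate named.

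**The concern.** Study treatment can affect creatinine only after randomisation. A change score that starts at admission adds whatever the kidney did beforehand, and an unadjusted t-test does not remove it. Creatinine change is the only renal outcome in the plan, so lost precision there makes a renal harm or benefit harder to see.

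The eligibility rule has the same timing problem. On a literal reading, a patient at 1.6 mg/dL on presentation and 2.6 mg/dL at randomisation (hypothetical values) may be enrolled although above the trial's own limit by then. This bears on who enters the trial, and so on the population for the primary analysis as well.

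**Working it through.** **1. Plan figures.** The documents give no standard deviation, expected difference or power for creatinine change or length of stay. The total of 150 rests on the primary success rates and plays no part here, so there is no plan figure to reproduce. Every standard deviation and correlation below is an assumption.

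**2. Formula.** Let s_pre be the SD of creatinine change from admission to randomisation, s_post the SD from randomisation to discharge, and ρ their correlation.

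- Variance of the change from admission = s_pre² + s_post² + 2ρ·s_pre·s_post
- Variance of the change from randomisation = s_post²

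**3. Results with s_post = 0.4 mg/dL (s_post² = 0.16).**

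| s_pre | ρ | Variance from admission | Effect of starting at randomisation |
|---|---|---|---|
| 0.1 | 0 | 0.01 + 0.16 = 0.17 | 0.01/0.17 = 5.9% lower |
| 0.2 | 0 | 0.04 + 0.16 = 0.20 | 0.04/0.20 = 20% lower |
| 0.3 | 0 | 0.09 + 0.16 = 0.25 | 0.09/0.25 = 36% lower |
| 0.1 | −0.25 | 0.17 − 0.02 = 0.15 | 0.16/0.15: 7% higher |
| 0.2 | −0.25 | 0.20 − 0.04 = 0.16 | no change |
| 0.3 | −0.25 | 0.25 − 0.06 = 0.19 | 0.03/0.19 = 16% lower |
| 0.2 | −0.5 | 0.20 − 0.08 = 0.12 | 0.16/0.12: 33% higher |

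For the raw change score the gain disappears at ρ = −s_pre/(2·s_post), which is −0.125, −0.25 and −0.375 for the three values of s_pre. If everyone is randomised on the day of admission, s_pre is essentially zero and so is the gain.

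**4. Power, under independence.** Take a two-sided 5% comparison that would have 80% power when measured from randomisation. Measured from admission, its power is Φ[(1.96 + 0.84)/√(1 + r²) − 1.96], with r = s_pre/s_post. For r = 0.25, 0.5 and 1.0 this gives about 78%, 71% and 51%.

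**5. Bias and type I error.** A simulation of 20,000 trials used 75 patients per arm, SD 0.3 mg/dL for each of two independent components, a mean pre-randomisation drift of 0.2 mg/dL in both arms, and the unadjusted t-test. With no treatment effect the rejection rate was 0.051. With a true difference of 0.15 mg/dL, the mean estimated difference from admission was 0.150. Power was about 58% from admission and 86% from randomisation. The earlier movement cost power but shifted nothing.

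**6. Length of stay.** If it were counted from admission, with an assumed SD of 5 days after randomisation and 1, 2 or 3 days before it, and independence, the avoidable share is 1/26 = 3.8%, 4/29 = 13.8% or 9/34 = 26.5%.

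**7. Eligibility.** This part needs no arithmetic. V.d.ii names presentation; V.a.i and V.b.i place screening, consent and randomisation afterwards; no section caps the interval or asks for a repeat value. Nothing written stops a patient from crossing the limit in between.

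**The case against.** The strongest reply is that the delay is assumed. The protocol recruits patients who arrive needing diuresis and start an intravenous course of at least 48 hours, which fits randomisation close to admission. The wording about presenting is also used in the inclusion criterion, so a site may read it as the patient's state when screened. VI.b adds daily laboratory monitoring and physician review. This stands in part: the size is unknown and may be nil. But nothing requires prompt randomisation, and an exclusion criterion that can be read two ways needs settling.

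A second reply is that independence favours the point. The creatinine at randomisation ends one change and begins the other, so measurement error in it pushes the correlation below zero, and a raw change from randomisation may then have the larger variance. This stands for the raw change score. For it to reverse the result, the admission value must track discharge better than the later value does, which is possible but not the usual pattern. Adjusting for baseline meets most of it, because the slope is estimated instead of fixed at 1.

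A third reply is that total hospital stay is a standard measure. That stands, and it is why the fix reports both versions.

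A fourth is that the presentation rule may be deliberately cautious, keeping out patients with recent renal impairment. The documents do not say. Applying the limit only to the later value would newly admit some of them, and that is the sponsor's clinical decision.

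**Conclusion.** The point holds as a matter of precision and of eligibility wording. Pre-randomisation creatinine movement counts in the renal outcome, the planned test does not remove it, and the renal limit is not tied to the time of randomisation. Under independence, with SDs of 0.4 mg/dL after and 0.1 to 0.3 mg/dL before randomisation, 6% to 36% of the variance is avoidable. That range rests on assumed SDs and an unknown delay. The gain is nil with same-day randomisation and may be nil or negative for a raw change score under negative correlation.

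Two stronger readings are not supported. A reader might infer that the reported renal difference is biased or cannot be interpreted as a treatment effect. Randomisation balances earlier change in expectation, so the between-arm difference stays valid; only the change within an arm mixes treatment with what came before. A reader might also infer that the plan counts length of stay from admission. That is the ordinary meaning of the term, but no start is written.

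The outcomes directly affected are secondary. The eligibility effect reaches the primary analysis only through who is enrolled, and the documents give no basis for quantifying it.

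**What to change.** - **V.e.ii, renal outcome.** Define it as the change from the last creatinine before randomisation to discharge.
- **VIII.a.** Compare arms with that baseline value as a covariate (analysis of covariance) in place of the unadjusted t-test for this outcome.
- **V.e.ii, length of stay.** State the start. Count days from randomisation to discharge and report total hospital stay alongside.
- **V.d.ii.** Keep the 2 mg/dL limit and have the sponsor confirm it against the last pre-randomisation value, within a window that the sponsor states, so that no one above the limit at randomisation is enrolled. The sponsor should also state whether patients who presented above the limit and have since fallen may enter.

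The cost is a few sentences. No new test is needed as long as the daily labs in VII.a are captured for the days before randomisation. A few patients become ineligible, and the renal result is slightly less comparable with studies that report change from admission to discharge.

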This study is a prospective trial however minimal risk to the patient is associated with participation in this study as he/she will be receiving one of two standard of care treatments at our center. Minimal risks associated with the study include experiencing common side effects from the FDA-approved medications used for treatment. The most common side effects of furosemide administered intravenously are low blood pressure, dizziness, headache, or irritation of the skin at the site of injection. In addition, the most common side effects of albumin administered intravenously are high blood pressure, headache, nausea/vomiting or irritation of the skin at the site of injection. There is also a potential risk for invasion of privacy since medical records will be accessed but all data will be de-identified to limit the chance of exposure of PHI.

b. Protection against risks

Physicians will be assessing patients in the study daily and will take precautions against the potential common side effects associated with the FDA-approved medications in this study as stated previously. Precautions include daily monitoring of patients through labs and physical examination and making medical interventions as deemed appropriate.

Data will be collected from the electronic medical record which will be de-identified and maintained in Research Electronic Data Capture (RedCap).

c. Potential benefits to subjects

Patients may benefit from taking part in this study. Based on experience with the use of furosemide (Lasix) and albumin in patients with similar conditions, researchers believe it

may be of benefit to people with cirrhosis. However, because individuals respond differently to therapy, no one can know in advance if it will be helpful for these patients. If the current therapy is not deemed helpful by the physician, the physician will start an alternative standard of care treatment for the patient.

d. Alternatives to participation

Patients may choose to not participate in this study. If participants choose to not participate in this study, the physicians will determine an alternative treatment plan for their fluid retention.

VII. Confidentiality of data and information storage

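### The weight limb of the primary outcome credits any 1 kg loss to the randomised strategy, with no rule for drained fluid or a switch to another diuretic

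*Combined protocol and SAP*

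**What the plan says.** - **Endpoint (V.e.i).** There are two limbs, and meeting either one is success: a urine output threshold of 0.5 ml/kg/hour, and "reduction in weight defined as weight loss of 1 kilogram or greater in a 24-hour period". The section does not say which 24 hours. Its explanatory note presents weight as a stand-in for how well the diuretic works, because urine collection is unreliable.
- **Population (V.d).** Patients enter with ascites, edema or effusions. The only exclusions are age, pregnancy and serum creatinine above 2 mg/dL. Drainage is not mentioned anywhere.
- **Other treatment (VI.b, VI.c).** Physicians may intervene as they judge necessary. If the therapy is not judged helpful, "the physician will start an alternative standard of care treatment for the patient". No rule says how such a patient is scored.
- **Data list (VII, item 4).** "Dose, frequency, and administration of furosemide" is collected, and the same item covers albumin. Drainage, other diuretics and the indication for albumin are not named.
- **Size and allocation (V.a).** "A sample size of 150 patients for this study was estimated", on an assumed "success rate of 70% in patients receiving diuretics alone and 90% in patients receiving diuretics plus albumin"; the error rates are given as "alpha = 0.05; beta =0.25". Each patient "will have 50% chance of being placed into either cohort". No blinding is described.
- **Analysis (VIII).** Groups are compared by chi-squared test at p<0.05.

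**The concern.** The trial asks whether adding albumin improves diuresis, but the weight limb measures net weight loss from any cause. The limbs are joined by an or, so a patient who fails on urine output and then has enough fluid drained to lose 1 kg is scored a success. A patient changed to another diuretic can likewise meet the criterion on a treatment that is not being tested.

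Section VI.c ties a change of treatment to poor response, so the patients affected are mainly those who would otherwise be failures. On the plan's own rates there are three times as many failures in control (30%) as in the albumin arm (10%), so equal conversion moves the control rate more and hides part of a real effect. In a trial with no described blinding, the decision to drain or switch could also depend on the arm.

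**Working it through.** **Inputs from the documents.** Success 70% v 90%; 150 patients, so 75 per arm at 1:1; alpha 0.05 (taken as two-sided, since this is not stated); beta 0.25, so target power 75%.

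**Inputs assumed.** The share of failures converted to success, s, and the share of controls given albumin, c. The documents give neither; 10% to 30% is used for illustration.

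**1. The plan's own figure.** With pooled variance under the null and pbar = 0.80:

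n per arm = [1.960 × sqrt(2 × 0.80 × 0.20) + 0.674 × sqrt(0.21 + 0.09)]² / 0.20² = 54.6, so 55 per arm and 110 in total, or 130 with continuity correction. The stated 150 is not reproduced; an unstated dropout allowance could explain it. The point here does not depend on this.

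Power at 75 per arm = Φ{[0.20 × sqrt(75) − 1.960 × sqrt(0.32)] / sqrt(0.30)} = Φ(1.138) = 87.2% (82.3% with continuity correction). The uncorrected 87.2% is the reference below.

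**2. Equal conversion in both arms.** Observed rate = p + s(1 − p).

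| s | Control | Albumin arm | Difference | Power |
|---|---|---|---|---|
| 0% | 70% | 90% | 20 points | 87.2% |
| 10% | 73% | 91% | 18 points | 82.5% |
| 20% | 76% | 92% | 16 points | 76.7% |
| 30% | 79% | 93% | 14 points | 69.9% |

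Power crosses the 75% target between s = 20% and s = 30%.

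**3. Unequal conversion.** With sC in control and sA in the albumin arm:

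Difference = (0.90 + 0.10 sA) − (0.70 + 0.30 sC) = 0.20 + 0.10 sA − 0.30 sC.

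The arms move together only if sA < 3 sC.

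- sC 20%, sA 10%: 76% v 91%, 15 points, power 70.0%.
- sC 10%, sA 30%: 73% v 93%, still 20 points, power 91.1%.
- sC 0%, sA 20%: 70% v 92%, 22 points; the arms move apart.

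**4. No true effect, 70% in both arms.** With sC 10% and sA 30%, control is 0.70 + 0.10 × 0.30 = 73% and the albumin arm 0.70 + 0.30 × 0.30 = 79%. The chance of a significant result favouring albumin is 13.5%, where a two-sided 5% test allows 2.5% in that direction.

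**5. Albumin given to controls.** This is contamination, not a scoring error. If a share c of controls responds at 90%, the control rate is 0.70 + 0.20c. For c of 10%, 20% and 30% it is 72%, 74% and 76%, with power 80.9%, 72.7% and 62.9%.

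**The case against.** The strongest reply is that this is an unstated detail, not a fault. The note in V.e.i makes the intent plain: weight change is meant to reflect diuretic response. If the scored window is the first 24 hours, treatment added later for poor response falls largely outside it. The data list cannot be exhaustive, because weight and urine output, which the endpoint needs, are also missing from it; the medical record is the source, and drainage could be looked up there. All the conversion rates are assumed, and at 10% or 20% power stays above the planned 75%.

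Much of this stands. It limits the size of the problem and rules out saying that the information is lost. It does not remove the problem: a stated intent is not a scoring rule, the window is not fixed, and nothing commits the team to collecting these events or treating them consistently.

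The objection also disposes of some stronger readings that a reader might infer:

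- That the arms are always pulled together. Step 3 shows that this depends on relative use in the two arms.
- That non-study albumin goes unrecorded, or is itself a success. Item 4 of the list includes albumin; only the indication is missing, and receiving it meets neither limb.
- That every drained patient becomes a success. Drainage acts only on the weight limb, and only if net loss reaches 1 kg within the period.

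**Conclusion.** The concern holds in this limited form. As written, the weight limb can score a non-responder who was drained or switched as a success of the randomised strategy, and the plan has no rule to prevent it. Under 70% v 90%, bias is towards no difference when conversion is equal or higher in control, and generally whenever conversion in the albumin arm is less than three times that in control. Beyond that ratio the difference grows, and with no true effect unequal use can produce a spurious one.

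The loss is 2 to 6 percentage points of difference, and about 5 to 17 points of power, for equal conversion of 10% to 30% of failures. These figures rest on assumed rates, a two-sided test without continuity correction and 75 evaluable patients per arm. They show sensitivity and do not predict what will happen. The documents do not establish that drainage or switching will be common. The change is worth making because the remedy is cheap and is best fixed before outcomes are known.

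**What to change.** No change to care is needed; these are scoring and recording rules.

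1. In V.e.i, state that the volume drained within the scored 24-hour window is added back to the weight (1 litre taken as 1 kg) before the weight limb is scored. This requires the protocol to say which 24 hours are scored.
2. In VII, add drainage volume, other diuretics and the indication for albumin, each with times, taken from the existing record.
3. In VIII, state that all patients are analysed in their randomised arm.
4. Pre-specify one sensitivity analysis that scores as failure any patient who had drainage or a new non-study diuretic before meeting the criterion. It counts against whichever arm had more of these events, so it should accompany the primary analysis and not replace it.
5. Report non-study albumin in control descriptively, as contamination, and do not score it as failure, because that would penalise mainly the control arm. For example, with no true effect at 70%, if an assumed 20% of controls received it before meeting the criterion and independently of response, control would score 0.70 × 0.80 = 56% against 70%, a false benefit of albumin.

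The cost is a few form fields, slightly more chart abstraction, a few sentences of text and somewhat lower observed success rates.

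### The renal secondary outcome is a valid but unadjusted change in creatinine; adding admission creatinine as a covariate needs no new data and may sharpen it, by an amount the documents do not fix.

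*Combined protocol and SAP*

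**What the plan says.** The secondary outcomes in section V.e.ii include "Change in renal function as defined by a chance in serum creatinine from admission to discharge". It is the only renal outcome listed.

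Section VIII.a does not pair tests with outcomes. It states that "Student's t-test will be used to compare continuous variables" and assigns chi-squared to categories. No covariate is named anywhere, so the natural reading is an unadjusted t-test on the change.

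Three other passages matter:

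- Section V.a.i: each patient "will have 50% chance of being placed into either cohort".
- Section V.a.ii: "A sample size of 150 patients for this study was estimated", on assumed response rates of 70% and 90%. This is about 75 patients per arm, sized on response and not on creatinine.
- Section V.d.ii: a patient "who presents with a serum creatinine greater than 2 mg/dL will be excluded". Admission creatinine is therefore known at screening. Section VII.a also lists "Daily lab results including chemistry panel, INR, liver function tests, renal function tests" among the data collected.

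**The concern.** A t-test on the raw change subtracts the whole admission value from the discharge value, which fixes the baseline coefficient at 1. Regression estimates that coefficient from the data. If the true slope of discharge on admission creatinine is not 1, the fixed coefficient leaves explainable variation in the error term, and the confidence interval is wider than the same data allow.

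The same residual term carries chance imbalance. If the arms differ by D in mean admission creatinine, the change score passes (rho × k − 1) × D into the observed treatment difference. The multiplier is −0.5 at rho 0.5, k = 1, and −0.3 at rho 0.7, k = 1.

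At stake is the precision of the trial's one renal comparison, in a trial whose size was not chosen with that comparison in mind.

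**Working it through.** **Inputs.** From the documents: 1:1 allocation and 150 patients (V.a), the change outcome (V.e.ii), the t-test (VIII.a). Not in the documents, so assumed: rho and k, taken as common to both arms.

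**The plan's own figure.** No SD, correlation or power is stated for creatinine, so there is nothing to reproduce for this outcome. The 150 belongs to the primary outcome. From 70% versus 90%, two-sided 0.05 and 75% power I get 110 in total, or 130 with continuity correction, not 150. That is a separate matter; 150 is used here only as the number of patients.

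**Step 1: variances.** With the admission SD set to 1, the variance of the treatment-effect estimate is proportional to:

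- change score: 1 + k² − 2·rho·k
- adjusted for admission creatinine: k²(1 − rho²)

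The first minus the second is 1 − 2·rho·k + rho²k² = (1 − rho·k)², which is never negative. Adjustment therefore never loses in large samples, and ties only at rho·k = 1.

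**Step 2: ratio of adjusted to change-score variance.**

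| k | rho 0.5 | 0.6 | 0.7 | 0.8 | 0.9 |
|---|---|---|---|---|---|
| 0.8 | 0.571 | 0.602 | 0.628 | 0.640 | 0.608 |
| 1 | 0.750 | 0.800 | 0.850 | 0.900 | 0.950 |
| 1.25 | 0.893 | 0.941 | 0.981 | 1.000 | 0.950 |
| 1.5 | 0.964 | 0.993 | 0.998 | 0.953 | 0.777 |
| 2 | 1.000 | 0.985 | 0.927 | 0.800 | 0.543 |

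Example, k = 1 and rho = 0.5: 0.75 / (2 − 1) = 0.75. The confidence interval is 1 − √0.75 = 13.4% narrower, equal to the precision of 150 / 0.75 = 200 patients under the unadjusted method.

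Over rho 0.5–0.9 and k 1–1.5 the reduction is nil to 25%. At k = 0.8 it is 36–43%. At rho 0.9 and k = 2 it is 46%.

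Simulation with 75 per arm and k = 1 gave reductions of 25.0%, 13.8% and 4.0% at rho 0.5, 0.7 and 0.9, against 25%, 15% and 5% from the formula.

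**Step 3: cost of estimating the slope.** With 75 per arm and a normally distributed baseline, the average inflation is 1 + 1/(150 − 4) = 1.0068, or about 0.7%. Because chance imbalance varies, simulation puts it above 2.6% in 5% of trials and above 4.6% in 1%.

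**Step 4: skewed values under the entry limit.** Assume lognormal creatinine with median 1.0 mg/dL, log-SD 0.3–0.5 at both times and log-scale correlation 0.5–0.9, with admission values above 2 mg/dL removed.

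- As stated: k 1.02–1.36, ratio 0.78–0.98. False-positive rates at nominal 5% were 4.7–5.1% adjusted and 4.7–5.2% for the t-test on change.
- Discharge log-SD at 75% of the admission log-SD: k 0.75–0.96, reduction 29–49%.
- Discharge value doubled in 10% of patients: ratio 0.92–1.00. Tripled: 0.97–1.00.

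**The case against.** The strongest reply is that nothing in the plan is wrong. Randomisation makes the t-test on change unbiased, its standard error already allows for chance imbalance, and its error rate holds in the simulations. The outcome is one of several secondary outcomes, and no decision rule depends on it. All of this stands, and it is why the point is an option and not a correction.

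The second reply is that the size of the gain comes from assumptions. This also stands. A reader might take 25% as the expected gain or as a ceiling; the table shows it is neither. A reader might also infer that the 2 mg/dL limit forces k above 1 and so rules out the larger gains at k = 0.8. The limit narrows admission values and so raises k relative to an untruncated sample, but k exceeds 1 only if the discharge spread is otherwise about as large. The documents say nothing about that spread.

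Third, a few large rises, which a renal safety comparison exists to detect, could reduce the gain to almost nil. That is correct, and the support for the untransformed scale in Step 4 covers false-positive rates only for smooth lognormal data.

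Last, the change score already subtracts admission creatinine, so the imbalance argument reaches only the residual linear part, proportional to (1 − rho × k), and vanishes when rho × k = 1. It would be wrong to infer that the planned comparison is biased by baseline.

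None of these replies removes the large-sample result, or the fact that the covariate is already in hand.

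**Conclusion.** The point holds as an optional efficiency improvement to a valid secondary analysis. In large samples, adjusting for admission creatinine is at least as precise as the planned test, and strictly more precise unless rho × k = 1. The reduction in the variance of the treatment-effect estimate is nil to about 25% if rho is 0.5–0.9 and k is 1–1.5. Both are assumptions; outside them it can be larger, and with a heavy tail of creatinine rises it can be near nil. Against this stands an average variance cost of about 0.7% at 150 patients. No figure in the plan is shown to be wrong, and the primary outcome is untouched.

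**What to change.** Add to section VIII.a: *Discharge minus admission serum creatinine (mg/dL, untransformed) will be compared between arms by linear regression on arm with admission creatinine as a covariate.*

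The outcome in V.e.ii stays as it is. Regressing discharge creatinine instead of the change gives the same arm coefficient and standard error. Naming the model and scale in advance also closes off a choice between adjusted and unadjusted results once the data are seen.

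The cost is one sentence. Every patient with a change value already has the admission value, so no data are added and nobody is lost by adjusting. The SPSS package named in VIII.a fits the model. The downside is the small loss in Step 3 if the covariate explains nothing beyond the subtraction, somewhat larger in a trial with marked chance imbalance at baseline.
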